Description of Study Intervention:	Radiotracer production: Blue Earth Diagnostics Ltd, manufacturers of ¹⁸ F-rhPSMA-7.3, has pledged support with gratis radiotracer unit doses supplied from PET-NET Solutions, a commercial radiopharmacy who made similar unit doses under IND #141561 for the Phase 3 trial also completed at our center. This study IND #162587 is held by [name].
Study Duration:	5 years

1.4 1.2 Schema

1.5 1.3 Schedule of Assessments

Procedures	Enrollment/Screening (-30 days)	Study Visit 1 PET/CT 1 (Within 30 days of enrollment)	(Study Visit 2 PET/CT 2 (Within 2-7 days of Visit 1)	Follow up (1-3 business days after each PET/CT)
Informed consent	X			
Demographics	X			
Pertinent Medical history	X			
Administer study intervention		X	X	
AE assessment		X	X	X
Complete Case Report Forms (CRFs)	X	X	X	X

2. Objectives (and Endpoints)

OBJECTIVES	ENDPOINTS

Primary
 
1. To determine if administering 20 mg furosemide IV at the time of radiotracer injection significantly reduces bladder activity compared with the same patient scanned without furosemide as internal control
 
20 patients with biochemical recurrence of prostate cancer following radical prostatectomy will be sequentially assigned to either undergo 18F-rhPSMA-7.3 PET/CT without furosemide first followed by a second PET/CT with furosemide at 2-7 days afterward, or vis-versa (10 in each group). Patients will be encouraged to void during the uptake phase up to 15 minutes before being placed on the scanner for imaging. Bladder activity (SUVmax, SUVmean, and bladder volume), ureteral activity (SUVmax, SUVmean), as well as renal activity (SUVmax, SUVmean), will be recorded. The presence and degree of halo artifacts around the bladder and kidney will also be recorded. Exclusion criteria for this trial will include urinary incontinence that may interfere with performing the study and contraindications to furosemide. As always, patients will be encouraged to arrive well hydrated and to drink an additional 500-1000 ml of water during the uptake phase.
	Determine the difference in the urinary bladder activity on ¹⁸ F-rhPSMA-7.3 PET/CT with furosemide compared with ¹⁸ F-rhPSMA-7.3 PET/CT without furosemide in biochemical recurrence of prostate cancer post radical prostatectomy (Specific Aim 1).

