¹⁸F-rhPSMA-7.3 PET/CT Imaging: PET/CT will be acquired on a state-of-the-art GE Discovery 690 TOF PET-CT scanner at Emory University Hospital or similar device. Patients do not need to fast prior to the scans. All patients will receive one PET/CT scan with 20mg furosemide administered intravenously at the time of radiotracer administration and will be encouraged to orally hydrate with 500-1000mL of water during the uptake phase of 60-70 minutes. Patients will be encouraged to void during the uptake phase up to 15 minutes prior to the commencement of the scan, if possible. PET images will be acquired from proximal thigh to skull base, approximately 3 minutes per bed position. All PET scans will be acquired in a 3-dimensional mode and the emission data will be corrected for randoms, dead time, scatter and attenuation. The images will be reconstructed using an iterative algorithm. Vital signs will be measured before and after administration of the radiotracer.

End of Study Definition

The study will be closed to recruitment once all 20 patients have been recruited, scanned with the 2 PET/CTs each and have completed follow-up (1-3 business days after each PET/CT). The study will be formally closed once all manuscripts have been published and all follow-up completed. There will be no other study-specific visits after the second PET/CT scan (visit 2), though the patient will be called by the study nurse within 1-3 business days after each study to ensure no delayed AEs occurred. The follow-up phone call for one study will be performed before the patient undergoes the subsequent scan.

3.3 5.2 Dosing and Administration

IV injection of 8 mCi (296 MBq) \pm 20% of rhPSMA-7.3 (¹⁸F) diluted up to 10 mL will be used for each of the two PET scans. This dose is based on dosimetry data obtained from published phase I study data [21], and the dose utilized in the approval phase III trial that was recently concluded [[NCT04186845](#)]. The study will be performed under IND #162587 held by [name].

3.4 5.3 Risks and/or adverse events

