- Radiation Risks: The principal risk associated with a radiation dose is the possibility of developing radiation-induced cancer later in life. However, the additional risk of radiation-induced cancer from these diagnostic procedures is low compared to the risks from the disease itself. Human dosimetry data for 18F-rhPSMA-7.3 from the phase I study of Tolvanen and co-workers[18]: The (radiation absorbed) effective dose from the administration of 225 MBq of 18F-rhPSMA-7.3 is 0.0138 mSv/MBq at a 1-hour voiding interval. The organs with the highest absorbed radiation dose are the adrenals (0.184 mGy/MBq), the kidneys (0.172 mGy/MBq), and the submandibular glands (0.148 mGy/MBq). The effective dose from the CT component of the study is 15.7mSv.
- Allergic or other reactions to radiotracer: The risk of AEs and SAEs from PET radiotracers is exceedingly low. A significant shift from baseline can be attributable to the radiotracer injection and not the patient's medical condition will be considered an unexpected AE. An event greater than 24 hrs will not be considered related to study procedure AE since the radiotracer has effectively decayed by 20 hours. There have been no previous instances of allergic reactions. In prior studies where 18F-rhPSMA-7.3 was used in human subjects, the risk of adverse events which can be attributed to the radiotracer is extremely low, and of minimal medical impact such as burning at IV site or headache.
- Risks related to IV for PET scan: A small amount of radioactive material will be injected by either a hand-held needle or a machine. Such injections are generally quite safe, but any injection involves some risks. The injection could harm a nerve, artery, or vein, or cause infection. The radioactive material could also leak from veins, causing swelling and discomfort.
- False positive on PET: It is possible that a lesion identified on the experimental PET procedures may be false-positive, thus potentially leading to an inappropriate biopsy. While further evaluation of imaging finding to confirm true positivity may occur according to the standard of care practice, a biopsy of the imaging-identified lesion is not in the scope of this trial, nor is it a requirement.

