- Furosemide: The risk from the low dose (20mg) of furosemide is minimal. It will temporarily cause increased urination. Though unlikely, other side effects may include: nausea or vomiting, diarrhea, constipation, stomach cramping, vertigo, dizziness, headache, blurred vision, itching or rash.

3.5 5.4 Dose Modification

Not applicable

3.6 5.5 Concomitant medication

Not applicable

3.7 5.6 Study Procedures

Screening Phase

Adult patients with biochemical recurrence of prostate cancer, status post prostatectomy who meet the eligibility criteria will be enrolled in the study.

Inclusion Criteria

- i. Adenocarcinoma of the prostate, post-prostatectomy.
- ii. Biochemical recurrence of prostate cancer following RP with or without adjuvant or salvage therapy: PSA ≥ 0.1 ng/mL
- iii. Age over 18.
- iv. Ability to provide written informed consent.
- v. Patients with standard of care creatinine ≤ 1.3 mg/dL performed within 90 days prior to enrollment

Exclusion Criteria

- i. Inability to undergo ^{18}F -rhPSMA PET-CT, contraindications to furosemide or urinary incontinence that may interfere with performing the study.

Study population:

- Y 1. Adult patients with a diagnosis of adenocarcinoma of the prostate, post radical prostatectomy
- Y 2. Biochemical recurrence as defined by PSA ≥ 0.1
- Y 3. Age over 18 years and ability to give informed consent
- N 4. Inability to undergo ^{18}F -rhPSMA-7.3 PET/CT
- N 5. Contraindications to furosemide such as true allergy or urinary incontinence that may interfere with performing the study

3.8 5.7 Description of Study Procedures

Overall Design

We will undertake a study with 20 patients with biochemical recurrence of prostate cancer status post radical prostatectomy. Consideration for inclusion in this study will be based on a detectable serum PSA after radical prostatectomy (PSA ≥ 0.1 ng/ml).

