
*For international studies, you are required to engage a CRO that is working in the site country and/or to consult with Emory's legal counsel regarding compliance with the country's clinical research regulations.
			

Patients will be monitored by the technologists and/or study nurse before and after the studies for any adverse events/reactions. They will be given contact phone numbers to call if they experience any problems (i.e., problems with the IV site, any allergic reaction symptoms). Basic monitoring of adverse events during the 18F-rhPSMA-7.3 PET visit will be performed. This will consist of direct observation by our study staff during the visit with documentation of any adverse events or lack thereof in the electronic medical record. The physical half-life of the radiotracer is 110 minutes. Hence, adverse events are not expected to occur past 24 hrs after radiotracer administration.

Written IND safety reports will be submitted to the FDA by the IND sponsor, for serious, unexpected suspected adverse reactions within 15 calendar days of learning of its occurrence. If the event is fatal or is deemed to be life threatening, the report will be made within 7 calendar days. The IND sponsor will also make an assessment of whether the event constitutes an unanticipated problem posing risks to subjects or others (UP). This assessment will be provided to the Emory University IRB, which, in turn will make a final determination. If the Emory IRB determines an event is a UP it will notify the appropriate regulatory agencies and institutional officials.

In addition to reporting of Serious Adverse Events (SAEs) to the responsible IRB/IEC and Health Authority, Principal Investigator or designee will inform Blue Earth Diagnostics (BED) of all SAEs in connection with the Study that occur following receipt of rhPSMA-7.3, whether or not related to Product. PI or designee shall notify BED within twenty-four (24) hours of knowledge of any SAEs. SAE reports to BED must be recorded and faxed or scanned and emailed to:

Bracco Diagnostics Inc. Drug Safety Unit
E mail: [contact]
[contact]

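### The 24-hour cut-off for calling an adverse event related rests on tracer decay alone, but its wording covers the whole study procedure, including the IV injection and furosemide

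*Combined protocol and SAP*

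**What the plan says.** The rule stands in Section 5.3, in the bullet on reactions to the radiotracer, and again in Section 9, item 2: "An event greater than 24 hrs will not be considered related to study procedure AE since the radiotracer has effectively decayed by 20 hours". The monitoring text in Sections 11 and 12 gives the half-life as 110 minutes and continues: "Hence, adverse events are not expected to occur past 24 hrs after radiotracer administration". That sentence shows that time of onset is meant, not duration.

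Other parts of the plan bear on it:

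- **Follow-up call.** The End of Study Definition says "the patient will be called by the study nurse within 1-3 business days after each study to ensure no delayed AEs occurred". The Schedule of Assessments has a matching column with AE assessment and CRF completion.
- **IV risks.** Section 5.3 says of the injection: "The injection could harm a nerve, artery, or vein, or cause infection".
- **Furosemide risks.** The list in the same section ends with "constipation, stomach cramping, vertigo, dizziness, headache, blurred vision, itching or rash".
- **Unanticipated problems.** Sections 11 and 12 adopt the OHRP definition. It needs at least a reasonable possibility that the research caused the event, and it sets no time limit.
- **IND safety reports.** These are sent "for serious, unexpected suspected adverse reactions within 15 calendar days of learning of its occurrence".
- **Reports to the tracer manufacturer.** These cover "all SAEs in connection with the Study that occur following receipt of rhPSMA-7.3, whether or not related to Product".
- **Analysis.** Section 11.1 defines a safety set but marks safety analyses as not applicable.

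**The concern.** The conclusion of the rule is wider than its reason. The reason is radioactive decay. The conclusion covers the study procedure, which is an IV injection of tracer in both scans plus IV furosemide in one. Furosemide is what the trial is testing, so its adverse events should not be attributed by the half-life of a different product.

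The rule also works against the follow-up call. The call exists to find delayed events, yet an event that began after 24 hours has its relation settled before anyone looks at it. That conflicts with the possible-link test in the unanticipated-problem definition.

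What is at stake is the judged relation of late events, chiefly non-serious ones. Two expedited routes could also be touched. The 15-day FDA report needs a suspected reaction and the unanticipated-problem report needs a possible link, and an automatic finding of unrelated would remove both.

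**Working it through.** **1. The plan's own decay figure.** The half-life is 110 minutes (Sections 11 and 12) and the administered activity is 296 MBq (Section 5.2). The fraction left after t minutes is 0.5^(t/110).

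- 20 h: 1200/110 = 10.9 half-lives; 0.5^10.9 = 0.052%; about 0.15 MBq of 296 MBq.
- 24 h: 1440/110 = 13.1 half-lives; 0.5^13.1 = 0.011%; about 0.034 MBq.

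The plan's statement about decay is reproduced. As a statement about radiation it is sound.

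**2. What decay does and does not limit.**

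| Component | Risk named in the plan | Limited by decay? |
|---|---|---|
| Tracer, as a radiation source | Radiation | The remaining activity, yes |
| Tracer, as an injected substance | Allergic or other reaction | No |
| IV injection | Infection; nerve or vessel injury | No |
| Furosemide | Rash, itching, constipation and others | No |

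The plan gives no separate attribution rule or time window for the last two rows. It also gives no onset times for furosemide effects, so nothing here shows that late effects are common. The point is only that decay cannot rule them out.

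**3. How often the call falls beyond the cut-off.** The assumptions are mine: scans on Monday to Friday, and calls at the same clock time as the injection. Calendar days from scan to call are:

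| Call made at | Mon | Tue | Wed | Thu | Fri | Later than 24 h |
|---|---|---|---|---|---|---|
| 1 business day | 1 | 1 | 1 | 1 | 3 | 1 of 5 |
| 2 business days | 2 | 2 | 2 | 4 | 4 | 5 of 5 |
| 3 business days | 3 | 3 | 5 | 5 | 5 | 5 of 5 |

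The total is 1 + 5 + 5 = 11 of 15 combinations. The call for one scan must precede the next scan, so after a first scan with a short gap the later call days may not be available. The count does not adjust for that. It counts scheduling combinations, not adverse events.

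**4. Exposure.** The rule applies to 20 men × 2 scans = 40 planned injections, 20 of them with furosemide.

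**5. What the rule does not catch.** An event that began within 24 hours and is first reported at the call is outside the cut-off and can still be judged related.

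**The case against.** The best defence is context. The sentence sits in a bullet about tracer reactions, follows a sentence on tracer injection and argues from tracer decay. The IV and furosemide have their own bullets without a cut-off. Sections 11 and 12 state an expectation, not a rule. A sensible investigator may read the sentence as tracer-only. That narrower reading is possible, but the wording is not limited to the tracer. Even a tracer-only reading leaves a non-radiation reaction to the injected substance excluded on time alone.

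The defence is strongest on consequences, where three larger conclusions are tempting:

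- **A serious late event would reach neither the FDA nor the IRB.** The documents do not support this. Sections 11 and 12 refer to SAE reporting to the IRB and health authority with no relatedness condition. The manufacturer receives every SAE after tracer receipt, with an investigator's causality assessment and the time from administration to onset. Only the 15-day and unanticipated-problem routes need a link. Both also need the event to be unexpected, and infection and rash are listed risks, so such an event would have to be unexpected in some other way, for example in severity.
- **Late events would be lost.** They would not. AE assessment and CRFs are scheduled at the call, and the monitoring table in Section 11 has the DSMC reviewing documentation of all adverse events biannually.
- **The trial would report a zero count of delayed related events.** No such count is planned, because Section 11.1 plans no safety analysis.

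**Conclusion.** The rule is wrong as written, in a limited sense. Its arithmetic is right, but a radiation argument is used to exclude relation to everything in the procedure. Read literally, it makes every event with onset after 24 hours unrelated, in the period the follow-up call is meant to cover, and it conflicts with the possible-link test elsewhere in the plan.

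The effect falls mainly on attribution of non-serious adverse events, with a possible effect on the two expedited routes. Bladder activity, detection and reader-confidence results do not change, nor do power or type I error. The 11 of 15 figure rests on the assumed weekday schedule and call time. The conclusion itself rests on the literal wording; if the sentence is confined to the tracer, what remains is the non-radiation reaction to the injected substance. The CRF is not among the documents, so how relation is recorded in practice cannot be checked.

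**What to change.** 1. In Section 5.3 and Section 9, item 2, replace the sentence with text such as: *Each AE reported up to the follow-up call is judged case by case for its relation to the radiotracer, furosemide (furosemide scan only), the IV procedure and the patient's condition, using the possible-link test in the unanticipated-problem definition. Time since injection is considered, but never decides the matter alone.*
2. In Sections 11 and 12, limit the 24-hour statement to radiation from the tracer.
3. Optional and secondary: in Section 11.1, replace the entry that marks safety analyses as not applicable with a descriptive listing, in the safety set, of all AEs up to the follow-up call. List them by scan (with or without furosemide), with onset time after injection and judged relation, and without a test.

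The cost is a few reworded sentences, a case-by-case judgement at a call already planned and, if item 3 is taken up, one short listing. No patients, visits or calls are added.

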
which increased progressively thereafter. The renal urinary excretion of ¹⁸F-rhPSMA-7.3 was lower compared with excretion of other PSMA ligands such as ⁶⁸Ga-PSMA-11 and ¹⁸F-DCFPyL, but higher than that of ¹⁸F-PSMA-1007[10]. Continued effort geared towards a further reduction in the urinary excretion of ¹⁸F-rhPSMA-7.3 is pertinent to improve detection rates.

Forced diuresis with co-administration of furosemide and the radiotracer is a strategy that has been explored in decreasing the urinary activity of other PSMA radioligands with a urinary route of excretion. In a study comparing the local prostate bed recurrence detection between patients who received hydration and furosemide administration at the time of ⁶⁸Ga-PSMA-11 injection versus patients who did not, Uprimmy et al. reported a higher local prostate bed recurrence detection in patients who received hydration with intravenous furosemide versus patients who did not (25.5% versus 17.3%, p=0.048)[14]. The frequency of equivocal findings for prostate bed recurrence was more prevalent among patients who did not receive furosemide injection compared with those who did (16.8% versus 12.3%). Lower urinary activity did not influence the intensity of tracer uptake in prostate cancer recurrent lesions between the two groups with comparable SUV max in recurrent lesions. Similar improved diagnostic confidence with the assessment of disease in the prostate bed has been reported in other studies[15]. In an analysis of data from Technical University of Munich, a cohort of 17 patients imaged with ¹⁸F-rhPSMA-7 (White Paper Prepared for Syncona: Evaluation of ¹⁸F-rhPSMA7, Unpublished) demonstrated bladder SUVmean mean (SD) (range): 4.57 (6.4) (1.4-28.8). Yet as shown in a subanalysis, this lower bladder activity is highly dependent on the use of furosemide. Mean bladder SUV mean (n=5) without furosemide is 9.24, while with furosemide (n=12), bladder SUVmean is 2.63. In the joint guidelines of the European Association of Nuclear Medicine (EANM) and the Society of Nuclear Medicine and Molecular Imaging (SNMMI), the use of furosemide was recommended for ⁶⁸Ga-PSMA-11 PET/CT imaging of prostate cancer[16].

2.3 3.1 Study Rationale

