Clinical trial performance and fidelity to the protocol will be monitored by the DSMC of Winship Cancer Institute of Emory University. The integrity of the data will be maintained by rigorous peer-review internally by all the clinical co-investigators in Radiation Oncology, Radiology/Nuclear Medicine, Surgical Oncology, and Medical Oncology.

Provisions to Protect the Privacy Interest of Participants

To maintain patient confidentiality, medical records will be accessed only by IRB-approved study personnel (e.g. CRC). A partial HIPAA waiver will be obtained to allow screening of provider schedules for the identification of potentially eligible research subjects. Upon medical record review and identification of a potentially eligible research subject, the patient's full name, MRN, EMPI, and full dates (e.g., DOB, procedure dates, admission dates, etc.) will be stored on a screening log and used by study coordinators for the subsequent study activities. The screening log will be kept on the HIPAA compliant shared folder and will be accessible only to limited IRB-approved study personnel (e.g., CRC). Sensitive data will always be stored on the HIPAA compliant shared folder and will never be stored on local or portable drives that are not encrypted per Emory IS standards.

Each study participant will be assigned a unique study identification (ID) number at the time that informed consent is given. Personal identifying information and study data, including the unique study ID, will be entered in the Microsoft Database that will be kept on the HIPAA compliant shared folder accessible to approved study personnel only. Only de-identified data will be shared with those outside the study team to ensure adequate protection of sensitive data.

Study identifiers will be kept indefinitely.

To maintain participant confidentiality, no identifying information about any of the study participants will be published. Any data published (including demographic information about the study sample as a whole) will be in aggregate/summary form only.

11.1 Statistical consideration section:

The objective of this early phase study is to determine if administering 20mg furosemide IV at the time of radiotracer injection significantly reduces bladder activity compared with the same patient scanned without furosemide as control.

Sample size determination

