We will image 20 patients with biochemical recurrence of prostate cancer post-prostatectomy for this study. Based on prior observation, we assume an SUV mean of 9.2 (SD=11.1) in those receiving 20mg furosemide IV at the time of radiotracer injection, and an SUV mean of 2.6 (SD=1.0) in those not receiving furosemide (White Paper Prepared for Syncona: Evaluation of 18F-rhPSMA7, Unpublished). Assuming a correlation between paired measurements of 0.5 which results in a standard deviation of change in SUV mean of approximately 10, we have 80% power to detect that change in SUV mean (9.2 vs. 2.6) with 20 patients, assuming a Type I error of 0.05, using a paired t-test. The sample size was calculated using PASS 2020 v20.0.3.

Populations for analyses

Efficacy set: All patients administered both 20mg furosemide IV at the time of radiotracer injection and without furosemide.

Safety set: All patients receive a dose of the radiotracer with each study.

Statistical analyses:

General Approach

Continuous variables will be summarized using mean, median, interquartile range, standard deviation, and min/max. Categorical variables will be summarized using frequencies and percentages. All tests will be two-sided with an alpha level of 0.05, unless otherwise noted. Testing assumptions will be

assessed and verified. Statistical analysis will be conducted using SAS 9.4 (SAS Institute Inc., Cary, NC).

Analysis of the Primary Efficacy Endpoint

Change in bladder SUV mean: The primary endpoint is change in bladder activity, as measured by bladder SUV mean, between administration of 20mg furosemide IV at the time of radiotracer injection and without furosemide. Change in bladder SUV mean will be assessed using a paired t-test, or using a non-parametric equivalent such as a Wilcoxon signed rank test. Descriptively, change in bladder SUV mean will be reported for those administered 20mg furosemide IV at the time of radiotracer injection first (Group A), and those administered 20mg furosemide IV at the time of radiotracer injection second (Group B).

Analysis of the Secondary Endpoints:

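### The sample-size paragraph's own inputs give about 75% power, not 80%, and its furosemide labels are the reverse of the Background's

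*Combined protocol and SAP*

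**What the plan says.** The sample-size paragraph in section 11.1 sets two planning values, both attributed to an unpublished white paper. The first reads "we assume an SUV mean of 9.2 (SD=11.1) in those receiving 20mg furosemide IV at the time of radiotracer injection"; the second, for the comparison scan, reads "an SUV mean of 2.6 (SD=1.0) in those not receiving furosemide". It goes on: "Assuming a correlation between paired measurements of 0.5 which results in a standard deviation of change in SUV mean of approximately 10". The conclusion is "we have 80% power to detect that change in SUV mean (9.2 vs. 2.6) with 20 patients", with a Type I error of 0.05 and a paired t-test. The General Approach in the same section adds "All tests will be two-sided with an alpha level of 0.05, unless otherwise noted".

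The Background (section 2) summarises the same white paper. For the cohort of 17 patients it "demonstrated bladder SUVmean mean (SD) (range): 4.57 (6.4) (1.4-28.8"), and it splits them as follows: "Mean bladder SUV mean (n=5) without furosemide is 9.24, while with furosemide (n=12), bladder SUVmean is 2.63". The objective at the head of section 11.1 is to find out whether furosemide "significantly reduces bladder activity compared with the same patient scanned without furosemide as control".

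**The concern.** Two things in this paragraph disagree with the plan's own figures.

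- **SD of change.** It is presented as the result of the two SDs and the correlation, but those inputs give a larger value. If the power was computed from the smaller one, it is overstated.
- **Labels.** Taken literally, the planning values have furosemide raising bladder SUVmean about 3.5-fold (9.2 / 2.6), whereas the trial is designed to show a reduction and the cited data are reported elsewhere as showing one.

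This paragraph is the plan's only justification of the sample size. A report that takes its design statement from here would give a power that the inputs do not deliver and prior data pointing the wrong way.

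**Working it through.** **Inputs.** From section 11.1: means 9.2 and 2.6, so a difference of 6.6; SDs 11.1 and 1.0; correlation 0.5; n = 20; alpha 0.05, two-sided; paired t-test. From the Background: 9.24 (n = 5, without furosemide), 2.63 (n = 12, with furosemide), and overall 4.57 (SD 6.4), range 1.4 to 28.8. There is no allowance for dropout, and none is needed here, because a patient who misses the second scan is replaced (Withdrawal of Participants).

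**1. Reproducing the stated 80%.** Paired t-test power comes from the noncentral t distribution with 19 degrees of freedom and noncentrality (difference / SD of change) × √20. With an SD of change of 10, the noncentrality is 0.66 × 4.472 = 2.95 and power is 79.95%. This matches the plan.

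**2. SD of change from the stated inputs.**

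SD of change = √(11.1² + 1.0² − 2 × 0.5 × 11.1 × 1.0) = √(123.21 + 1.00 − 11.10) = √113.11 = 10.64

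With these SDs no correlation gives 10: the smallest possible value, at correlation 1, is 11.1 − 1.0 = 10.1.

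**3. Power at that SD.** The noncentrality is (6.6 / 10.635) × 4.472 = 2.78 and power is 74.95% (75.1% with the unrounded difference 9.24 − 2.63 = 6.61).

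| Setting (n = 20, two-sided paired t-test) | Power |
|---|---|
| SD of change 10, as stated | 79.95% |
| SD of change 10.64, from the inputs | 74.95% |
| SDs 11.05–11.15 and 0.95–1.05, difference 6.5–6.7, correlation 0.5 | 73.1% to 76.8% |
| As the row above, with correlation 0.45–0.55 | 72.7% to 77.2% |
| SDs and difference as printed, correlation anywhere from 0 to 1 | 71.0% to 79.2% |

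Rounding of the inputs therefore does not recover 80%. At an SD of 10.64, 22 patients give 79.3% and 23 give 81.2%.

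**4. Which labels are right.** Pool the two groups using the Background's group sizes.

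- *Background labels*: n = 5 with 9.24 (SD 11.1), n = 12 with 2.63 (SD 1.0). Mean = (5 × 9.24 + 12 × 2.63) / 17 = 4.57. Sum of squares = 4 × 11.1² + 11 × 1.0² + 5 × (9.24 − 4.574)² + 12 × (2.63 − 4.574)²; divided by 16, the square root is 6.41. The reported summary is 4.57 (6.4).
- *Section 11.1 labels*: n = 5 with 2.63 (SD 1.0), n = 12 with 9.24 (SD 11.1). Mean = 7.30, SD = 9.73. Neither matches.

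Both the means and the SDs in section 11.1 therefore sit under the wrong label.

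**5. Effect of the labels on power.** Reversing the labels changes the sign of the difference and leaves its size and the SD of change alone. With a two-sided test, power stays at 74.95%. The whole shortfall comes from the SD.

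**6. How firm the SD of 11.1 is.** In 12 values with mean 2.63 and SD 1.0, none can exceed 2.63 + 11/√12 = 5.81, so the cohort maximum of 28.8 belongs to the group of 5. The other four then average (5 × 9.24 − 28.8) / 4 = 4.35. If all four were exactly 4.35, the SD would be 10.9. A single patient can account for almost all of it.

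**The case against.** The arithmetic and the label contradiction are not in dispute. The case against giving them much weight runs as follows.

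- **Loose rounding.** The plan says approximately 10, and the correlation of 0.5 is itself assumed; the two source groups were different patients and cannot inform it. This is fair, but the rounded figure is the one that yields the stated 80%, and with the printed SDs no correlation from 0 to 1 gets there.
- **Other routes to 80%.** At an SD of 10.64, a two-sided normal approximation gives 79.3% and a one-sided t-test 84.8%. The plan names a paired t-test and two-sided testing, so neither is its stated method.
- **75% is not the trial's likely power.** This stands. SUVmean cannot be negative, so a mean of 9.2 with an SD of 11.1 implies strong skew. As an illustration resting on an assumption outside the documents, simulated paired lognormal data with these means and SDs and a correlation near 0.5 gave t-test power of about 96%, and Wilcoxon power above 99%; the plan permits a Wilcoxon signed rank test. The 75% is what the paragraph's own normal-theory calculation gives, and no more.
- **Is 20 still enough?** Under the paragraph's assumptions, 80% would need 23 patients. Whether about 75% on that conservative basis is acceptable is the sponsor's decision. With an SD this uncertain, the calculation is a weak reason to change enrolment either way.
- **The direction is clear elsewhere.** True: the Background, the hypothesis and the objective all say reduction, so misreading is unlikely. The planning values are still wrong as written.

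**Conclusion.** Both errors hold, and they are independent. Under the paragraph's own assumptions (difference 6.6, SDs 11.1 and 1.0, correlation 0.5, normally distributed changes, two-sided 0.05 paired t-test, 20 patients), power is about 75% rather than 80%, a shortfall of 5.0 points due entirely to using 10 where the inputs give 10.64. The furosemide labels are reversed against the Background, at no cost in power. Neither error undermines the choice of test or endpoint. The 75% depends on an SD estimated from 5 patients, probably driven by one high value, and on normality; it corrects the stated figure and should not be read as a forecast. This should be fixed, as two plain errors in the sole justification of the sample size that are cheap to remove.

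**What to change.** Replace the planning statement in section 11.1 with wording to this effect: SUVmean 9.2 (SD 11.1) without furosemide and 2.6 (SD 1.0) with furosemide; a correlation of 0.5 gives an SD of change of 10.6; under these assumptions 20 patients give about 75% power with a paired t-test at two-sided alpha 0.05.

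Add a sentence saying that the SD of 11.1 rests on 5 patients and that the calculation assumes normally distributed changes, so the power is approximate. If the sponsor wants to keep 80% as a formal target, the paragraph should say why 20 patients remain adequate.

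The cost is a wording change to the protocol. The stated power drops by about 5 points. The correction does not itself require more patients, and it leaves the test, the endpoint and data collection as they are.
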